Unfortunately, no standard recommendations exist to guide clinicians in management of bronchorrhea resistant to standard interventions. Systemic glucocorticoids (in addition to aerosolized ones), macrolide antibiotics, and scopolamine patch (a systemic anticholinergic) have been routinely used by intensivists in such situations. Remarkably, little data exist on the use of systemic glucocorticoids and macrolides in ventilated patients, and most of the knowledge is provided by clinical trials assessing long-term effects of such agents in patients with underlying chronic respiratory diseases¹⁵. Most data on effectiveness of scopolamine is limited to case reports describing its use in palliative care.

Octreotide is another agent with mucoregulatory properties. It is a synthetic analogue of a hormone somatostatin and functions as an anti-secretory drug by inhibiting synthesis of pituitary and gastrointestinal hormones. One of the hormones inhibited by octreotide is secretin - a potent stimulant of electrolyte and water movement in the gastrointestinal system. As lungs have secretin receptors too, it has been suggested that inhibiting secretin also reduces chloride and water efflux from bronchial epithelial cells, thereby reducing sputum production ^{8,9,10}. In fact, several case reports have emerged about its effectiveness in cancer patients with bronchorrhea ^{8, 11, 12}. Remarkably, these case reports demonstrated its effectiveness in patients who failed to respond not only to the standard treatments but also to systemic glucocorticoids and scopolamine. For instance, Hudson et al. described the successful use of octreotide (300-500 mcg/24 hrs) through subcutaneous route to manage the symptoms of bronchorrhea in a 74-

year-old female with bronchioloalveolar cell carcinoma ⁸. The patient was producing more than 1 L of sputum per day and after two days of octreotide therapy, sputum production subsided completely. Pahuja et al. reported similar results with octreotide administered as intravenous infusion, in a 47-year-old female with bronchioloalveolar cell carcinoma ¹¹.

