As described above, scopolamine is one of the interventions routinely used by intensivists to manage excessive bronchial secretions in patients who have failed the standard measures. Similarly to octreotide, it inhibits both bronchial and gastrointestinal secretions. Remarkably, in a recent randomized control, octreotide was shown to be superior to scopolamine for symptom control in patients with increased gastrointestinal secretions due to bowel obstruction ^{13,14}.

Given the fact that no quality evidence-based information is available to guide ICU clinicians in management of bronchorrhea that has failed to respond to standard interventions, as well as the promising results described in case reports, we propose a randomized controlled trial that would compare effectiveness of octreotide to other interventions that have been used to control bronchial secretions in mechanically-ventilated patients.

Octreotide is widely available and has a relatively low cost (about \$17/day in our hospital). In the United States, it has been used widely in outpatient and inpatient settings for over 16 years, mostly for various endocrinopathies and gastrointestinal variceal bleeds but also for a number of other pathologies. It is considered by clinicians to be an overall well-tolerated medication, with fewer significant side-effects compared to systemic steroids and scopolamine. If octreotide is proven to be an effective mucoregulator, it may become an essential tool used in the intensive care units throughout the world.

Objectives/Purpose of the study:

The purpose of this study is to evaluate effectiveness of including parenteral octreotide (12-25 mcg/hour for 72 hours) in addition to the other standard of care treatments deemed necessary by the ICU attending physician in managing bronchorrhea in mechanically ventilated patients. It is hypothesized that octreotide decreases excessive bronchial secretions and shortens time to extubation.

Trial Design:

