Also, subjects in both groups will be at risk that their bronchial secretions are not well controlled. However, it is expected that at the time of enrollment, the subjects will already be receiving nebulizer treatments, which is the standard of care for management of mechanically ventilated patients; the study will compare additional interventions for which no quality evidence-based data exists so far.

Subjects may benefit from this study by experiencing better control of their bronchial secretions, which may shorten duration of mechanical ventilation and decrease risk for related complications. The information learned from this study may help other patients requiring mechanical ventilation.

Selection and Withdrawal of Subjects:

Inclusion criteria:

- Patients are being weaned from mechanical ventilation
- Excessive bronchial secretions (over 200 ml/24 hours) is deemed by the Primary Team to be a major barrier to extubation

Exclusion criteria:

- Known hypersensitivity to octreotide
- Persistent bradycardia (HR < 60)
- Mobitz type II or 3rd degree heart block in patients without a pacemaker
- Active septic shock
- Patients being treated with intravenous agents for hypertensive urgency or emergency
- Cardiac surgery patients
- Initiation of therapy with systemic or inhaled steroids within 72 hours prior to screening*
- Initiation of therapy with systemic or inhaled anticholinergics within 48 hours prior to screening*
- Patients receiving cyclosporine, bromocriptine, or drugs with low therapeutic index that are mainly metabolized by CYP3A4

*Initiation of aerosolized (inhaled) anticholinergics or steroids will not be withheld to qualify a subject for the study. Once a mechanically ventilated patient has been on an anticholinergic for more than 48 hours or a steroid for more than 72 hours, he or she will no longer meet that exclusion criteria and may be included in this study with appropriate debriefing about the study by the study team to the patient or their authorized representing and obtaining informed consent.

Withdrawal of subjects:

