Baseline volume of bronchial secretions suctioned over a 24-hour period will be recorded for all subjects, and interventions prescribed by the random treatment assignment will be initiated and continued for up to 72 hours. Simultaneously, the rate of secretions will be measured and recorded (by registered nurses taking care of the patients) during each 24-hour shift. Volume of normal saline used to flush endotracheal tube will be recorded and then subtracted from the total volume found in the suction container in the end of each shift. Effectiveness of the interventions studied in this trial will be determined by comparing the percent change in the secretions rate (relative to the baseline rate) between the “Octreotide” and “Routine group” subjects, which will be the primary outcome. The secondary outcome will be the percentage of patients who were extubated within 72 hours after initiating the interventions (“Octreotide” vs “Routine”).

Assessment of Safety:

The study will be performed in mechanically ventilated patients in an ICU, an environment where close monitoring of all patients in an absolute requirement. Similarly to the patients in the control arm, subjects in the treatment arm will be closely monitored for adverse reactions of octreotide. Close monitoring includes continuous and periodic monitoring of vital signs including Heart Rate, Blood Pressure and Respiratory Rate. Based on these data, as well as results of serum chemistry performed at least daily (which is part of the standard care in ICU), doses of beta-blockers, calcium channel blockers, insulin, and agents to control fluid and electrolyte balance will be adjusted, - similarly to situations when octreotide is used for other medical conditions.

Given the reported adverse reactions of octreotide, an electrocardiogram will reviewed for each subject, and patients with bradycardia and significant conduction defects will be excluded (see the exclusion criteria). During the study, vital signs will be monitored every hour, and cardiac activity will be continuously monitored by telemetry. To confirm timely assessment of safety,

the study team will ensure that the vital signs data are recorded every 4 hours in the data collection tool.

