If a patient develops bradycardia (HR < 60 bpm), octreotide administration will be stopped and the patient will be withdrawn from the study. Furthermore, if a subject experiences increase in systolic BP to 180 mmHg or above, octreotide administration will be stopped and the patient will be withdrawn from the study. However, if a subject experiences increase in systolic BP by at least 40mmHg over 2 hours, the infusion rate will be decreased to 12 mcg/hr; the BP will be reassessed every hour, and the infusion rate will be titrated up as tolerated to a maximum of 25mcg. Given octreotide's effect on serum glucose level, all subject's capillary blood glucose (CBG) will be monitored every 4 hours to monitor for hyperglycemia and hypoglycemia. The glucose levels every 4 hours will be recorded in the data collection form. Subjects who are hyperglycemic and require more than 20 units of intravenous insulin per hour will be withdrawn from the study, as will subjects who experience hypoglycemia (CBG < 60 mg/dL) despite being on 5% dextrose drip.

Statistical analysis:

Data will be analyzed with the assistance of a statistician at Danbury Hospital's Department of Research and Innovation. The differences between the two groups (Routine Care vs. Octreotide) in the percentage change of rate of secretion (defined as milliliters per 24 hours) for each of the 24-hour periods as compared to the baseline 24-hour period and proportion of patients extubated within 72 hours (defined as both time to extubation AND yes/no extubated within 72 hours) will be compared. The Fisher's exact test will be used to assess statistical significance (alpha set at $p < 0.05$). If the sample size allows and there are adequate cell frequencies, regression analyses will be used to assess the association between the use of Octreotide and the primary outcome variables.

Given that no previous research has been conducted to examine management of bronchorrhoea resistant to conventional interventions in mechanically ventilated patients, a power calculation to estimate the sample size cannot be performed reliably. We do recognize the small sample size to be included in our study and intend for this project to serve as a pilot study that would provide some evidence-based information to guide clinicians at our institution in such situations and provide background information for further studies on a much larger scale.

References:

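### The primary secretion comparison names no primary 24-hour period and no single value per patient, so its day-2 and day-3 estimates are, by inference, not comparisons of the randomised groups

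*Combined protocol and SAP*

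**What the plan says.** Assessment of Efficacy makes the percent change in secretion rate from baseline the primary outcome, with no time point and no summary over the 72 hours. Statistical analysis then compares the arms on the "percentage change of rate of secretion (defined as milliliters per 24 hours) for each of the 24-hour periods". It states that Fisher's "exact test will be used to assess statistical significance", with alpha at 0.05. It gives no primary day, 72-hour mean, repeated-measures model or rule for several tests. Regression is mentioned only if the sample size allows.

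On measurement, Assessment of Efficacy says: "Volume of normal saline used to flush endotracheal tube will be recorded and then subtracted from the total volume found in the suction container". Trial Design ends the study interventions, and the recording of concomitant care, at 72 hours, extubation or withdrawal, whichever is first. No rule covers a 24-hour period cut short by either event.

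On the link with extubation, the inclusion criteria require: "Excessive bronchial secretions (over 200 ml/24 hours) is deemed by the Primary Team to be a major barrier to extubation". The Objectives add: "It is hypothesized that octreotide decreases excessive bronchial secretions and shortens time to extubation". Assessment of Safety withdraws patients when octreotide is stopped for certain adverse reactions. Extubation within 72 hours is analysed as a separate outcome, both as time to event and as yes/no.

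**The concern.** Taken together, these sections imply that a patient contributes secretion volumes only while intubated and in the study. If octreotide works as hypothesised, responders leave first and more leave from the octreotide arm. Some octreotide patients also leave through drug-linked withdrawal. The day-2 and day-3 comparisons are then conditioned on something that happens after randomisation and depends on both outcome and treatment.

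The plan calls itself a pilot, gives no power calculation, and intends to "provide background information for further studies on a much larger scale". What is at stake is therefore the effect estimate it hands on, more than its power. In addition, with three period-specific results and none named primary, the headline day can be chosen after the data are seen.

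**Working it through.** **Plan's own figure.** There is none to reproduce. The plan gives 15 per arm and alpha 0.05, but no effect size, SD, power or extubation rate. All inputs below are assumptions, and the results are illustrations. Truth means the suctioned volume had everyone stayed intubated. No withdrawals are simulated.

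**Model A (proportional effect).**
- Log ratio to baseline on day d: L = b + e_d + ln(1 - effect_d), with SD of b 0.5 and SD of e_d 0.3.
- Probability of extubation in each period: 1/(1 + exp(s(L - ln m))), with m = 0.5 or 0.7. Here s sets how strongly secretions drive extubation. Since the documents do not give it, s = 0.5, 1, 2 and 4 were all run.
- Extubation falls at the period end, or at a random hour h (0.5 to 24) with volume scaled to 24 h and extra mean-preserving log noise of variance 0.09(24/h - 1).
- 200,000 simulated patients per arm.
- The mean ratio without an effect is exp((0.25 + 0.09)/2) = exp(0.17) = 1.185. The day-3 truths are 1.185 × 40 = 47.4 (constant 40%), 1.185 × 0.5 × 60 = 35.6 (half the arm responds by 60%), 1.185 × 60 = 71.1 (building 10/40/60%) and 1.185 × 20 = 23.7 (waning 60/40/20%).

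Day-3 difference in percentage points, patients still intubated against truth, over all settings:
- Constant 40%: -40 to -52 against -47.
- Half respond: -9 to -31 against -36, so about -10 to -30. The weakest link (s = 0.5) gives about -30 and the strongest (s = 4) gives -9 to -15.
- Building: -76 to -85 against -71.
- Waning: -24 to +12 against -24.

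With the constant effect, 4.5 to 10.9 of 15 controls and 3.4 to 6.5 of 15 octreotide patients remain on day 3. Day 1 gives about -47 (constant) and -35 to -36 (half respond), which is essentially the truth.

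**Model B (additive effect, threshold extubation).** SD 30 points, between-day correlation 0.6, control mean change -10. A patient is extubated after a day on which the change reaches -50, -40 or -30.
- True -20: about -20 on day 1, -13 to -16 on day 2, -11 to -14 on day 3. About 9.5 to 12.8 controls and 5.3 to 9.5 octreotide patients remain.
- True -30: -16 to -20 on day 3.
- True 0: within 0.2 points on every day.

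A constant, uniform effect is thus nearly preserved in some settings of Model A and roughly cut by a third to a half in Model B. Neither the size nor the direction of the bias can be read from the documents.

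**Multiplicity.** Three independent tests at 0.05 give 1 - 0.95^3 = 14.3%. With t-tests at between-day correlations of 0.3, 0.5 and 0.7, the chance of at least one false positive is about 14%, 12% and 11% (9% at 0.9). With Mann-Whitney in Model A it is 10 to 12%. Fisher's exact test needs a cut-off that the plan does not state. Assuming a reduction of at least 50% or at least 30%, it gives about 1 to 5% over the three periods.

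**The case against.** The strongest reply is that this is a declared pilot, that extubation is analysed in its own right, and that day 1, which the plan also reports, is nearly unbiased. Much of that stands. It does not say who enters the secretion comparison on days 2 and 3 or which day carries the conclusion, and the plan still tests each period at 0.05.

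Four stronger readings are tempting but not supported.
- **That the plan states that only intubated patients are compared.** It does not. This is inferred from how volume is measured and from when the interventions stop. Chart review might recover volumes for withdrawn patients who are still intubated, but the plan does not say these would be used.
- **That the bias runs one way, or is small whenever patients respond alike.** The models above disagree on both.
- **That a follow-on trial would be mis-sized many times over.** At a fixed SD, planning on -9.2 to -31.4 in place of -35.6 gives (35.6/31.4)^2 = 1.3 to (35.6/9.2)^2 = 15 times the needed size. But this assumes that the planner uses day 3 alone and that only half the arm responds.
- **That the false-positive rate is 14%.** Fisher's exact test is the only test named and is conservative at 15 per arm. The higher figures need a test that the plan does not name.

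Two further discrepancies are wording matters. Trial Design allows up to 24 hours for baseline when describing length of participation, while Assessment of Efficacy specifies a 24-hour period. Readings are twice daily in one part of Trial Design, but every 24 hours in its list of study-team duties and in Assessment of Efficacy. Twice-daily readings can be summed.

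**Conclusion.** The point holds as a gap in the definition of the primary outcome with a real consequence. Followed as written, the plan yields later-day contrasts that are, on a well-supported inference, not comparisons of the randomised groups, and it leaves the choice of headline day open. The structural point needs no assumed figures; any statement of size does. In the models tried, day 3 ranged from strong understatement through near accuracy to modest overstatement, and under a waning effect with a strong extubation link it changed sign. Where octreotide has no effect on secretions, Model B shows no such bias, though drug-linked withdrawals were not modelled. Multiplicity is a secondary matter. The plan should be changed, but the defect does not by itself undermine the pilot.

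**What to change.** Before any outcome data are seen:

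1. Name one primary variable, with one value per randomised patient who has a post-randomisation reading, and test only that at 0.05. One option is the percent change from baseline in net volume per 24 intubated hours, from a start point common to both arms until 72 h, extubation or withdrawal. Another, if the effect is expected to build, is the same rate over the last 24 intubated hours in that window. The Background cites a case in which "after two days of octreotide therapy, sputum production subsided completely". The sponsor should choose, and state the expected onset.
2. Record intubated hours with each reading.
3. Report single periods descriptively, with the number contributing by arm and a statement that days 2 and 3 are not comparisons of the randomised groups.
4. Report by arm any patient with no post-randomisation reading.
5. Align the wording on reading interval and baseline length across Trial Design and Assessment of Efficacy.

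The cost is SAP wording and one added data field; extubation time is already needed for the time-to-extubation outcome.

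No summary is unbiased if the effect changes over time. In Model A the time-normalised rate recovers the truth when half the arm responds (about -35 against -36) and when the effect is constant (-46 to -48 against -47). Under the building effect it gives about -23 to -37 against a 72-hour mean of 1.185 × (10 + 40 + 60)/3, about -43. Under the waning effect it overstates: -60 to -64 against 1.185 × 40, about -47. Extubation is also decided open-label by clinicians who may be investigators, which affects any of these variables.

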This study is an open-label, randomized controlled trial. Patients will be randomized into two groups of 15, "Routine Care" group, which will serve as the control group, and "Octreotide" group. The amount of bronchial secretions is routinely measured in all mechanically ventilated patients. Once the Primary Team identifies a patient as a candidate for the study, the study team will review their medical records and assess the patient based on the inclusion and exclusion criteria to determine if they are qualified to participate in the study (screening). If the patient is qualified, one of the study members will explain the research project to the patient or his/her authorized representative and also explain the informed consent process. This study does not compensate patients for participating in the study or for any potential injuries/illness arising out of their participation in this study. This aspect will be made clear to the patients (or their authorized representative) in addition to other risks and benefits of participation in this study. If the patient or his/her authorized representative agrees to participate in the study informed consent will be obtained. After informed consent, the patient will be administered

standard of care medications for the first 24 hours after the screening and a baseline volume of bronchial secretions during this 24 hour period will be recorded. Additionally, medications administered and procedures performed during this 24 hour period would also be recorded. Then, a security envelope containing group assignment will be opened by the ICU attending physician. Both groups will continue to receive treatments that have already been initiated to manage bronchial secretions. In addition, "Octreotide" group will receive parenteral octreotide, while "Routine Care" group will not receive any additional treatment for the study. All patients will continue to receive the care deemed necessary by the ICU attending physician and his/her team. These interventions will be continued for 72 hours or until extubation or withdrawal from the study, whichever occurs earlier. Subsequently, the standard of care management, as determined by the Primary Team, will be continued.

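### Time to extubation is a compared outcome with no method that can analyse it and no rule for patients not extubated; comparing only times seen within 72 h would dilute a real effect or reverse it.

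*Combined protocol and SAP*

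**What the plan says.** The Objectives section puts forward two effects of octreotide: less secretion and a shorter time to extubation.

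Assessment of Efficacy has one extubation outcome, and it is binary: "The secondary outcome will be the percentage of patients who were extubated within 72 hours after initiating the interventions". It does not list time to extubation.

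Statistical analysis takes the proportion extubated within 72 h and says it is "defined as both time to extubation AND yes/no extubated within 72 hours". Both parts are to be compared between groups. On method it says "The Fisher's exact test will be used to assess statistical significance", and then "If the sample size allows and there are adequate cell frequencies, regression analyses will be used to assess the association". That regression names no model, depends on sample size, and is directed at the primary outcome variables.

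On design, "Patients will be randomized into two groups of 15". On follow-up, "These interventions will be continued for 72 hours or until extubation or withdrawal from the study, whichever occurs earlier". Trial Design also provides for retrospective chart review over the whole stay. The section on withdrawal of subjects lets chart-review data be used after a subject chooses to leave.

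No section gives a time origin for the time variable, a censoring rule, a value for patients still ventilated at 72 h, a rule for death before extubation, or a rule for patients withdrawn early.

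**The concern.** A time cannot define a proportion, and Fisher's exact test cannot compare times. One of the two hypothesised effects is therefore attached to a variable that has no usable analysis.

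The gap matters because the easiest way to fill it is a poor one. The variable sits under a 72 h outcome and prospective recording ends at 72 h, so an analyst could readily compare the extubation times observed in that window. That keeps only patients who were extubated, and extubation is what treatment is meant to change. Extra patients whom octreotide gets off the ventilator late in the window would then raise its mean time. The Background gives some reason to consider a delayed effect: in one cancer patient, "after two days of octreotide therapy, sputum production subsided completely".

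The trial is a pilot, but one intended to guide clinicians at the institution and to inform larger studies. A wrong or weakened signal on time to extubation would affect both uses. The bracket also turns one secondary outcome into two.

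**Working it through.** There is no figure in the plan to reproduce. It states that "a power calculation to estimate the sample size cannot be performed reliably" and gives no extubation rates, so the rates below are assumptions.

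**Inputs.** From the plan: 15 patients per arm, a 72 h window and alpha 0.05 (two-sided assumed). Assumed: proportion p of controls extubated by 72 h = 0.30, constant control hazard, and hazard ratio 3 acting either from 0 h or from 48 h. Deaths and withdrawals are not modelled.

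**Formulas.** Control hazard λ = −ln(1 − p)/72. For a constant hazard h over a window of length W, the mean time among those extubated in the window is 1/h − W·e^(−hW)/(1 − e^(−hW)).

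**Control.** λ = 0.35667/72, so 1/λ = 201.9 h. Mean among the extubated = 201.9 − 72 × 0.70/0.30 = 33.9 h.

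**Immediate effect.** Proportion extubated = 1 − 0.70³ = 65.7%. Mean among the extubated = 67.3 − 72 × 0.343/0.657 = 29.7 h.

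**Effect from 48 h.**
- Still ventilated at 48 h: 0.70^(48/72) = 0.788. Extubated before 48 h: 0.212, mean 201.9 − 48 × 0.788/0.212 = 23.1 h (unrounded inputs).
- From 48 to 72 h the tripled hazard over 24 h gives survival 0.70. Extubated then: 0.788 × 0.30 = 0.237, mean 48 + 67.3 − 24 × 0.70/0.30 = 59.3 h.
- Total extubated: 44.8%. Mean = (0.212 × 23.1 + 0.237 × 59.3)/0.448 = 42.2 h (unrounded inputs).

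**Patients contributing to an extubated-only comparison.** Immediate effect: 15 × (0.300 + 0.657) = 14.4 of 30. Effect from 48 h: 15 × (0.300 + 0.448) = 11.2 of 30.

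**Simulated trials of 15 v 15.** The t-test uses only patients extubated within 72 h. The log-rank uses all 30, with the rest censored at 72 h.

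| | Immediate | From 48 h |
|---|---|---|
| Extubated by 72 h, octreotide v control | 65.7% v 30% | 44.8% v 30% |
| Mean among the extubated | 29.7 v 33.9 h | 42.2 v 33.9 h |
| Octreotide looks slower | about 37% | about 74% |
| t-test significantly in favour | about 5% | not quoted |
| t-test significantly against | not quoted | about 9% |
| Log-rank in favour | about 52% | about 11% |

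**Sensitivity.**
- With 40% of controls extubated and onset at 48 h, the means are 40.7 v 32.9 h and octreotide looks slower in about 75% of trials.
- With onset at 12 h the extubated-only means are nearly equal: 34.6 v 33.9 h at 30%, and 32.5 v 33.0 h at 40%.
- A different model has 30% in each arm extubated at 6–48 h, with octreotide adding 30% at 36–72 h. The means are 40.3 v 26.7 h. Octreotide looks slower in 94.7% of trials, and a Mann-Whitney test is significantly against it in 18.6%. The log-rank favours it in 27.7%. In three variants of this model octreotide looks slower in 89.7% to 94.6% of trials.
- Under proportional hazards with 30% v 60% extubated (hazard ratio 2.57), the means are 30.6 v 33.9 h. Mann-Whitney favours octreotide in 3.9% of trials, the log-rank in 39.4%.

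**The case against.** The strongest reply is that silence is not an instruction. A reader might infer that the plan compares only extubated patients. It does not say so: it says the groups will be compared, with a statistician's help. The t-test and Mann-Whitney test used above stand in for whatever an analyst might choose; neither is in the plan. This stands, and the point is worded as a gap that permits a misleading comparison.

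A reader might also infer that anyone ventilated at 72 h has no extubation time. Chart review over the whole stay may supply an extubation at, say, 90 h, including for patients who chose to leave. So the problem does depend on cutting times at 72 h. Only patients who die before extubation, or are never extubated in that stay, necessarily lack a time. The plan does not commit to using later times, so the gap remains.

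A third tempting reading is that an effective drug will look slower. That needs a late effect, or chance. An immediate effect keeps the right direction on average, and one case report showing complete resolution at two days does not show that nothing happens before 48 h. The 74% is also only the sign of a difference in means; a significant result in the wrong direction occurs in about 9%.

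Finally, the remedy does not rescue power if the effect is late: about 11% for the log-rank at 48 h onset. The 52% belongs to the immediate-effect case only.

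**Conclusion.** The concern holds in this limited form. The plan compares a time variable with no method that fits it and no rule for death, withdrawal or patients still ventilated, although a shorter time to extubation is hypothesised. If the gap were filled with times observed within 72 h, a large immediate effect would shrink to about 4 h (33.9 − 29.7 = 4.2) and be nearly undetectable. An effect beginning at 48 h would appear as about 8 h slower (42.2 − 33.9 = 8.3). These sizes rest on assumed extubation rates, a constant control hazard and a hazard ratio of 3; the direction depends on when the effect starts.

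It would be wrong to infer that the binary 72 h outcome is compromised. It can include every patient whose status is known, Fisher's exact test suits it, and this flaw does not touch it. The primary outcome is also outside this point. The correction should be made before the data are analysed, but it does not undermine the trial.

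**What to change.** In Statistical analysis:

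1. Take time to extubation out of the bracket. Keep yes/no extubated within 72 h, tested with Fisher's exact test, as the single secondary outcome, matching Assessment of Efficacy.
2. Add a separate supportive analysis of time to extubation in all 30 randomised patients: cumulative incidence curves by arm and a log-rank test.
3. State one time origin common to both arms, such as the opening of the envelope. Assessment of Efficacy counts from initiation of the interventions, so the text should acknowledge the difference or align the two.
4. Censor patients alive and still ventilated at 72 h at 72 h. Keep patients who die before extubation in the risk set to 72 h as not extubated, rather than censoring them at death.
5. Follow patients withdrawn from the study for extubation through the chart review already provided for. The withdrawal section says this for subjects who choose to leave; say that it also covers safety withdrawals.
6. Report the time analysis as descriptive.

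With complete follow-up to 72 h, each curve ends at that arm's yes/no proportion, so the two analyses cannot disagree about who was extubated. The cost is a few sentences and a little analysis time; extubation times and deaths should already be in the charts. The limitation is low power in a 30-patient pilot, which the change does not remove.
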